BP=blood pressure; CRC=clinical research center; HBsAg=hepatitis B surface antigen; HCV=hepatitis C virus; HIV=human immunodeficiency virus; PTH=parathyroid hormone

^a In the event a subject is prematurely discontinued from the study or withdraws, every attempt should be made to complete these assessments.

^b Vital signs will be obtained while subject is supine on study days noted. Temperature will only be taken at screening and predose on Day 1.

^c Height will be recorded at the screening visit only.

^d FSH (follicle stimulating hormone) is required at screening for all females. Serum β-hCG testing at timepoints indicated for all female subjects.

^e Drugs of abuse at screening and drugs of abuse and alcohol on Day -1.

Table 1 Schedule of Assessments

| Visit | Screening | Predose assessments | Treatment Period | | | | | | | | Follow-up ^h |
|-----------|------------|---------------------|------------------|---|---|---|---|---|---|---|------------------------|
| Study Day | -28 to -02 | -1 | 1 | 2 | 3 | 4 | 5 | 6 | 7 | 8 | |

^f Pharmacodynamic blood sampling assessments will include serum calcium and phosphate.

^g See [Table 2](#) and [Table 3](#) for detailed collection time points.

^h There will be a follow-up visit approximately 30 ±2 days following the last dose of investigational product.

ⁱ Non-Hispanic, Caucasian subjects only.

^j Subjects of Japanese descent only.

^k There must be a minimum washout period of 72 hours (maximum 73 hours) from dose to dose for the volunteers of Japanese descent.

^l SAEs will be followed to resolution (see Section [7.1.3](#))

Table 2 Detailed Schedule of Assessments (non-Hispanic, Caucasian Subjects)

| Study Day | Day 1 | | | | | | | | | | | | | | | | | | Day 2 |
|--|----------------|----------------|---|-----|-----|-----|-----|----|-------|------|----|------|----|----|----|----|-----|-----|-------|
| | Pre Dose 1 | Pre Dose 2 | 0 | 10m | 20m | 30m | 45m | 1h | 1.25h | 1.5h | 2h | 2.5h | 3h | 4h | 6h | 8h | 12h | 16h | |
| Hour (relative to dosing time) | | | | | | | | | | | | | | | | | | | |
| Physical examination ^a | | | | | | | | | | | | | | | | | | | X |
| Vital signs (BP, temperature and pulse) ^{a,b} | | X ^e | | | | | | X | | | | | | X | | X | | | X |
| TriPLICATE Electrocardiogram (12-lead) ^{a,c} | | X ^e | | | | | | | | | | | | | | | | | X |
| Biochemistry, hematology, and urinalysis ^a | | X ^e | | | | | | | | | | | | | | | | | X |
| Serum β-hCG Pregnancy test (females only) ^a | | | | | | | | | | | | | | | | | | | X |
| Investigational drug administration | | | X | | | | | | | | | | | | | | | | |
| Pharmacodynamic blood sampling ^d | | X ^e | | | | | | | | | | | | | X | | X | X | X |
| Anti-PTH antibody sampling | | X ^e | | | | | | | | | | | | | | | | | |
| Pharmacokinetic blood sampling | X ^f | X ^e | | X | X | X | X | X | X | X | X | X | X | X | X | X | X | X | |

BP=blood pressure; ECG=electrocardiogram; PK=pharmacokinetic, PTH=parathyroid hormone

^a In the event a subject is prematurely discontinued from the study or withdraws, every attempt should be made to complete these assessments.

^b Vital signs will be obtained while subject is supine at times noted. Temperature only to be obtained at screening and at predose on Day 1.

^c Electrocardiograms will be performed in triplicate at each timepoint.

^d Pharmacodynamic blood sampling assessments will include serum calcium and phosphate and must be drawn before PK samples at the same timepoint.

^e These assessments should be performed within 30 minutes prior to dose administration. The urine collection may be the first void of the day [providing that it is predose] but may be outside the 30 minute window if necessary.

^f These assessments should be performed within 90 (± 30) minutes prior to dose administration.

Table 3 Detailed Schedule of Assessments (Subjects of Japanese Descent)

| Study Day | Days 1, 4 and 7 | | | | | | | | | | | | | | | | | Days 2, 5 and 8 | |
|--|-----------------|----------------|---|-----|-----|-----|-----|----|-------|------|----|------|----|----|----|----|-----|-----------------|----------------|
| | Pre-dose 1 | Pre-dose 2 | 0 | 10m | 20m | 30m | 45m | 1h | 1.25h | 1.5h | 2h | 2.5h | 3h | 4h | 6h | 8h | 12h | 16h | |
| Physical examination ^a | | | | | | | | | | | | | | | | | | | X ^h |
| Vital signs (BP, temperature and pulse) ^{a,b} | | X ^e | | | | | | X | | | | | X | | X | | | X | |
| TriPLICATE Electrocardiogram (12-lead) ^{a,c} | | X ^e | | | | | | | | | | | | | | | | | X |
| Biochemistry, hematology, and urinalysis ^a | | X ^e | | | | | | | | | | | | | | | | | X |
| Serum β-hCG Pregnancy test (females only) ^a | | | | | | | | | | | | | | | | | | | X ^h |
| Investigational drug administration | | | X | | | | | | | | | | | | | | | | |
| Pharmacodynamic blood sampling ^d | | X ^e | | | | | | | | | | | | X | | X | X | | X |
| Anti-PTH antibody sampling | | X ^e | | | | | | | | | | | | | | | | | |
| Pharmacokinetic blood sampling | X ^f | X ^e | | X | X | X | X | X | X | X | X | X | X | X | X | X | X | X | |

BP=blood pressure; ECG=electrocardiogram; PK=pharmacokinetic, PTH=parathyroid hormone

^a In the event a subject is prematurely discontinued from the study or withdraws, every attempt should be made to complete these assessments.

^b Vital signs will be obtained while subject is supine at times noted. Temperature only to be obtained at screening and at predose on Day 1.

^c Electrocardiograms will be performed in triplicate at each timepoint.

^d Pharmacodynamic blood sampling assessments will include serum calcium and phosphate and must be drawn before PK samples at the same timepoint.

^e These assessments should be performed within 30 minutes prior to dose administration. The urine collection may be the first void of the day [providing that it is predose] but may be outside the 30 minute window if necessary.

^f These assessments should be performed within 90 (\pm 30) minutes prior to dose administration.

^h Serum β-hCG Pregnancy test (females only) and physical exam on Day 8 at discharge only.

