 - a) A subject of Japanese descent born in Japan, who has resided outside of Japan for no longer than 5 years and is of Japanese parentage, defined as having 2 Japanese parents, and 4 Japanese grandparents, all born in Japan.
 - b) A non-Hispanic, Caucasian subject who has 2 non-Hispanic, Caucasian parents and 4 non-Hispanic, Caucasian grandparents.

5. Male or nonpregnant, nonlactating female who agrees to comply with any applicable contraceptive requirements of the protocol or females of nonchildbearing potential.
6. Considered "healthy" by the investigator. Healthy status is defined by absence of evidence of any active or chronic disease following a detailed medical and surgical history, a complete physical examination including vital signs, 12-lead ECG, hematology, blood chemistry, and urinalysis.
7. Body mass index between 18.5 and 28 kg/m², inclusive, with a body weight ≥ 45 kg (99lbs). This inclusion criterion will only be assessed at the first screening visit.
8. Willing and able to consume standardized meals during the confinement period of the study. All participants will be required to consume the identical meals on study days when serial PK and PD blood samples are collected.
9. A clinical safety laboratory parameter of hemoglobin greater than 11.7g/dL (females) or 13.1g/dL (males) and less than 16g/dL (females) or 17.4g/dL (males) or, if out of this range, deemed not clinically significant by the principal investigator.
10. Total serum calcium within laboratory normal limits.
11. Serum parathyroid hormone (PTH) levels within laboratory normal limits.

Exclusion Criteria:

1. History of any hematological, hepatic, respiratory, cardiovascular, renal, neurological or psychiatric disease, gall bladder removal, or current or recurrent disease that could affect the action, absorption, or disposition of the investigational product, or clinical or laboratory assessments.
2. Current or relevant history of physical or psychiatric illness, any medical disorder that may require treatment or make the subject unlikely to fully complete the study, or any condition that presents undue risk from the investigational product or procedures.
3. Known or suspected intolerance or hypersensitivity to the investigational product(s), closely-related compounds, or any of the stated ingredients.
4. Significant illness, as judged by the investigator, within 2 weeks of the first dose of investigational product.

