5. Known history of alcohol or other substance abuse within the last year.
6. Donation of blood or blood products (eg, plasma or platelets) within 60 days prior to receiving the first dose of investigational product.
7. Use of the following prior to administration of investigational product within:
 - 30 days – loop diuretics, lithium, antacids, systemic corticosteroids (medical judgment is required by the investigator. Primarily high doses of systemic corticosteroids [eg, prednisone] should be excluded. Stable doses of hydrocortisone [eg, as treatment for Addison's disease] may be acceptable).
 - 3 months – calcitonin, cinacalcet hydrochloride, treatment with rhPTH(1-84) or N-terminal PTH or PTH-related peptide fragments or analogs
 - For females: changes in hormone replacement therapy within 3 months are excluded. Stable (≥ 3 months) hormone replacement therapy is acceptable.
 - 6 months – fluoride tablets, oral bisphosphonates, methotrexate, growth hormone, digoxin, raloxifene or similar selective estrogen receptor modulators (SERMs)
 - 12 months – intravenous bisphosphonates, drug or alcohol abuse, as determined by the investigator
8. Confirmed systolic blood pressure (BP) >139 mmHg or <89 mmHg, and diastolic BP >89 mmHg or <49 mmHg.
9. Twelve-lead ECG demonstrating measure of time between the start of the Q wave and the end of the T wave using Fridericia's formula in an electrocardiogram (QTcF) >450 msec at screening. If QTcF exceeds

450msec, the ECG should be repeated 2 more times and the average of the 3 QTcF values should be used to determine the subject's eligibility.

10. Positive screen for drugs of abuse at screening or drugs of abuse or alcohol on Day -1.
11. Male subjects who consume more than 21 units of alcohol per week or 3 units per day. Female subjects who consume more than 14 units of alcohol per week or 2 units per day. (1 alcohol unit=1 beer or 1 wine (5oz/150 mL) or 1 liquor (1.5oz/40 mL) or 0.75 oz alcohol).
12. Positive human immunodeficiency virus (HIV), hepatitis B surface antigen (HBsAg), or hepatitis C virus (HCV) antibody screen.
13. Use of tobacco in any form (eg, smoking or chewing) or other nicotine-containing products in any form (eg, gum, patch). Ex-users must report that they have stopped using tobacco for at least 30 days prior to receiving the first dose of investigational product.

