1.3 Risk/Benefit and Ethical Assessment

There is no anticipated benefit from taking part in this study.

Risks for subject exposure to rhPTH(1-84) are listed in the current investigator brochure and include, but are not limited to, the following:

- **Osteosarcoma:** In male and female rats, parathyroid hormone caused an increase in the incidence of osteosarcoma (a malignant bone tumor). The occurrence of osteosarcoma was dependent on parathyroid hormone dose and treatment duration. This effect was observed at parathyroid hormone exposure levels ranging from 3 to 71 times the exposure levels in humans receiving a 100 μ g dose of rhPTH(1-84). These data could not exclude a risk to humans. Because of a potential risk of osteosarcoma, it is recommended to use rhPTH(1-84) only in subjects with hypoparathyroidism who cannot be well-controlled on calcium and active forms of vitamin D alone and for whom the potential benefits are considered to outweigh this potential risk. Use of rhPTH(1-84) is to be avoided in subjects who are at

increased baseline risk for osteosarcoma such as subjects with Paget's disease of bone or unexplained elevations of alkaline phosphatase, pediatric and young adult subjects with open epiphyses, subjects with hereditary disorders predisposing to osteosarcoma or subjects with a prior history of external beam or implant radiation therapy involving the skeleton.

- Hypercalcemia during initiation of rhPTH(1-84) administration: In previous efficacy and safety studies in hypoparathyroidism, 29 of 121 (24.0%) rhPTH(1-84)-treated subjects experienced an on-treatment event of hypercalcemia. Monitoring of serum calcium during the treatment process can mitigate the risk, along with appropriate medical treatment.
- Hypocalcemia with abrupt withdrawal of rhPTH(1-84) therapy: In previous efficacy and safety studies in hypoparathyroidism, 24 of 121 (19.8%) subjects experienced a post-treatment event of hypocalcemia. Monitoring of serum calcium during the treatment process and after withdrawal can mitigate the risk, along with appropriate medical treatment.
- The safety of rhPTH(1-84) in pregnant or nursing women has not been established. Pregnancy tests will be performed on all females on 2 occasions prior to entering the treatment phase of the study, and at discharge after treatment and at follow-up. Both men and women must agree to adequate contraception methods (see Section 4.4) before taking part in the study.

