4.2 Exclusion Criteria

Subjects are excluded from the study if any of the following exclusion criteria are met:

1. History of any hematological, hepatic, respiratory, cardiovascular, renal, neurological or psychiatric disease, gall bladder removal, or current or recurrent disease that could affect the action, absorption, or disposition of the investigational product, or clinical or laboratory assessments.
2. Current or relevant history of physical or psychiatric illness, any medical disorder that may require treatment or make the subject unlikely to fully complete the study, or any condition that presents undue risk from the investigational product or procedures.
3. Known or suspected intolerance or hypersensitivity to the investigational product(s), closely-related compounds, or any of the stated ingredients.
4. Significant illness, as judged by the investigator, within 2 weeks of the first dose of investigational product.
5. Known history of alcohol or other substance abuse within the last year.
6. Donation of blood or blood products (eg, plasma or platelets) within 60 days prior to receiving the first dose of investigational product.
7. Use of the following prior to administration of investigational product within:
 - 30 days – loop diuretics, lithium, antacids, systemic corticosteroids (medical judgment is required by the investigator. Primarily high doses of systemic corticosteroids [eg, prednisone] should be excluded. Stable doses of hydrocortisone [eg, as treatment for Addison's disease] may be acceptable).
 - 3 months – calcitonin, cinacalcet hydrochloride, treatment with rhPTH(1-84) or N-terminal PTH or PTH-related peptide fragments or analogs
 - For females: changes in hormone replacement therapy within 3 months are excluded. Stable (≥ 3 months) hormone replacement therapy is acceptable.
 - 6 months – fluoride tablets, oral bisphosphonates, methotrexate, growth hormone, digoxin, raloxifene or similar selective estrogen receptor modulators (SERMs)

- 12 months – intravenous bisphosphonates, drug or alcohol abuse, as determined by the investigator

8. Confirmed systolic blood pressure (BP) $>139\text{mmHg}$ or $<89\text{mmHg}$, and diastolic BP $>89\text{mmHg}$ or $<49\text{mmHg}$.

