11.3 Vital Signs

Descriptive statistics for vital signs (systolic and diastolic blood pressure, pulse rate, and body temperature) and their changes from baseline at each post-baseline assessment and at the end of study will be presented by ethnic group and dose. All vital signs will be listed for each subject in the Safety Analysis Set.

Vital sign values will be considered PCI if they meet either the low or high PCI criteria listed in Table 5. The number and percentage of subjects with PCI values at each time point will be tabulated by ethnic group and dose. The percentages will be calculated relative to the number of subjects with baseline and at least 1 post-baseline assessment at that dose level and time point. The numerator is the total number of subjects with at least 1 PCI post-baseline vital sign value at that dose level and time point. A supportive listing of subjects with post-baseline PCI values will be provided including the subject number, ethnic group, dose, baseline, and post-baseline PCI values.

Table 5 Criteria for Potentially Clinically Significant Vital Signs		
Parameter	Classification (on CDRs)	Criteria
Systolic blood pressure (mm Hg)	HIGH and INCREASE	≥ 140 and increase of ≥ 20 from baseline value
	LOW and DECREASE	≤ 90 and decrease of ≥ 20 from baseline value
Diastolic blood pressure (mm Hg)	HIGH and INCREASE	≥ 90 and increase of ≥ 15 from baseline value
	LOW and DECREASE	≤ 50 and decrease of ≥ 15 from baseline value
Pulse rate (bpm)	HIGH and INCREASE	≥ 100 and increase of > 15 from baseline value
	LOW and DECREASE	≤ 45 and decrease of > 15 from baseline value
Temperature	HIGH	$> 38.3^{\circ}\text{C}$ or $> 100.9^{\circ}\text{F}$
	LOW	$< 35^{\circ}\text{C}$ or $< 95^{\circ}\text{F}$

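### Exclusion criterion 8 joins the systolic and diastolic limits with 'and', so one out-of-range pressure alone does not exclude a volunteer.

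*Protocol*

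**What the plan says.** Criterion 8 in the protocol synopsis reads "Confirmed systolic blood pressure (BP) >139 mmHg or <89 mmHg, and diastolic BP >89 mmHg or <49 mmHg". Section 4.2 has the same limits and the same connecting words, "and diastolic BP". The lead-in to Section 4.2 says "Subjects are excluded from the study if any of the following exclusion criteria are met", so one criterion is enough to exclude, but both pressures sit inside a single numbered criterion.

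Three other entry criteria touch on blood pressure without giving a number:

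- Inclusion criterion 6 requires the investigator to consider the subject healthy after an examination that covers vital signs: "Healthy status is defined by absence of evidence of any active or chronic disease".
- Exclusion criterion 1 covers a history of cardiovascular disease, among others.
- Exclusion criterion 2 covers disorders that may need treatment and "any condition that presents undue risk from the investigational product or procedures".

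Protocol Section 7.2.2.4 describes how screening pressure is measured and which arm is used. Its text does not say how the two limits combine. Its Figure 2, on screening vital signs, was not legible in the text I worked from.

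**The concern.** An eligibility rule should give the right answer when a site follows it to the letter. Here the letter of the rule asks for a systolic abnormality and a diastolic abnormality at the same time. An isolated high or low value of either pressure passes.

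The participants are healthy volunteers, and Section 1.3 of the protocol states: "There is no anticipated benefit from taking part in this study". In the readable text, criterion 8 is the only numeric blood-pressure limit for entry. If it does not apply, the decision rests on criteria without a threshold.

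The wording also leaves the site exposed either way. Section 10.2.2 makes the investigator responsible for enrolling only subjects who meet the criteria. A site that follows the text may admit someone the sponsor meant to keep out. A site that follows the presumed intent turns away someone who does not meet the written criterion, and Section 7.1.1.2 and exclusion criterion 15 do not allow a subject who failed screening to return.

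**Working it through.** The plan gives no figure to reproduce, so the check is a truth table.

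**Inputs** (criterion 8, synopsis and Section 4.2). Let S be true when systolic is >139 or <89 mmHg, and D be true when diastolic is >89 or <49 mmHg.

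- As written: exclude if S **and** D.
- Presumed intent: exclude if S **or** D.

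**Step 1: possible patterns.** Each pressure is low, in range or high, which gives 3 × 3 = 9 combinations. Systolic must exceed diastolic, so systolic <89 with diastolic >89 cannot occur: 9 − 1 = 8. One of these is fully in range, which leaves 8 − 1 = 7 out-of-range patterns.

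**Step 2: apply both rules.**

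| Systolic / diastolic | Example (mmHg) | 'And' (as written) | 'Or' |
|---|---|---|---|
| high / high | 165/95 | excluded | excluded |
| high / low | 150/45 | excluded | excluded |
| low / low | 85/45 | excluded | excluded |
| high / in range | 165/85 | not excluded | excluded |
| low / in range | 85/60 | not excluded | excluded |
| in range / high | 120/95 | not excluded | excluded |
| in range / low | 120/45 | not excluded | excluded |

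The written rule excludes 3 of 7 patterns and misses 4 of 7. With 'or', all 7 are excluded. A reading of 120/75 is accepted under both.

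**Step 3: try another parsing.** Ignore the comma and let 'and' bind more tightly than 'or'. The rule becomes systolic >139, or (systolic <89 and diastolic >89), or diastolic <49. The middle term is impossible, so what remains is systolic >139 or diastolic <49. That catches 165/85 and 120/45 but still misses 85/60 and 120/95: 5 of 7 patterns excluded, 2 missed. Neither parsing gives the rule that was presumably meant.

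**Step 4: look for the intent elsewhere.**

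- Section 7.2.2.4 calls for repeat measurements when the arms differ in either one of the two pressures.
- SAP Section 11.3, Table 5, gives systolic and diastolic pressure separate rows, each flagged by itself. That table concerns post-baseline values and also requires a change from baseline, so it does not conflict with criterion 8 and bears only on intent.
- Inclusion criterion 9 (hemoglobin) expressly lets the investigator's judgement override its numeric range. Criterion 8 has no such clause, which suggests a fixed limit was intended.

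**The case against.** The strongest reply is that this protocol sometimes uses 'and' to list alternatives. Exclusion criterion 10 excludes for a positive Day -1 result for drugs of abuse *or* alcohol, while Section 7.2.2.7 restates the rule with *and*; nobody would require both tests to be positive. Criterion 8 can be read the same way, as a list of excluded systolic values followed by a list of excluded diastolic values. The strict reading is also clinically implausible, since it accepts 180/85 mmHg, and an experienced Phase 1 site would probably apply 'or'. A confirmed 165/85 would in any case be hard to reconcile with inclusion criterion 6. Figure 2 might settle the matter, and no pharmacokinetic result depends on the word.

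Much of this stands. The intent was very likely 'or', the judgement-based criteria are a real safeguard, and the effect on the primary comparison is nil. It is also fair that 4 of 7 is not a miss rate. But loose usage in Section 7.2.2.7 shows what was probably meant, not what criterion 8 says. There, criterion 10 itself is worded correctly; here the operative criterion is the one with the wrong connective, in both places where it appears. The safeguards leave the threshold to each investigator, although the sponsor chose to set one.

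**Conclusion.** The concern holds: the criterion is wrong as written. Followed exactly, it does not exclude a volunteer with a single out-of-range pressure, which is 4 of the 7 possible out-of-range patterns. How many volunteers this would involve cannot be derived from the documents.

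The conclusion rests on the ordinary reading of the sentence, with the comma grouping the two systolic limits and the two diastolic limits. It also assumes that Figure 2 does not state a different rule; if it does, the figure and the criterion need to be reconciled.

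The point matters for volunteer safety and for consistent screening. It does not touch the sample size, the pharmacokinetic comparison or dose proportionality. It should be corrected, but it does not threaten the trial's conclusions.

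**What to change.** In the synopsis and in Section 4.2, reword criterion 8 to: *Confirmed systolic BP >139 mmHg or <89 mmHg, or confirmed diastolic BP >89 mmHg or <49 mmHg.* Repeating 'confirmed' makes clear that it applies to both pressures. Check that Figure 2 agrees.

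The cost is one connecting word and one repeated word in two places. The numeric limits, the measurement procedures, SAP Table 5 and all analyses stay unchanged.
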